4.6 RATIONALE FOR STUDY

This is a Phase I/IIa, first in man, dose escalation study with a one-year follow-up duration, designed to assess whether SAR421869 is safe, well tolerated and efficacious in patients with moderate to severe RP associated with Usher syndrome Type 1B.

Evaluation of a safe and effective dose of SAR421869 in this study will enable optimum dose identification and further characterization of the safety profile in the target population in Phase II/III efficacy studies.

4.7 RATIONALE FOR SAR421869

Usher syndrome Type 1B is a severely debilitating disease resulting in significant hearing loss at birth and progressive blindness. There are no treatments currently available and none in development.

The underlying cause of the retinal pathology of Usher syndrome Type 1B is mutations in the unconventional myosin VIIa gene (MYO7A). It is believed that by replacing the mutated gene in the RPE, with the corrected gene using SAR421869, that this deficiency will be corrected, and that the treatment of RP associated with Usher syndrome Type 1B with SAR421869 will result in a substantial alteration of the pathophysiology of the disease leading to attenuation of the deterioration in vision which is associated with the syndrome.

4.8 RATIONALE FOR INJECTION INTO THE EYE

The eye is a suitable target organ for gene therapy due to the following:

- The eye is easily accessible to the surgeon compared to other organs, both in terms of administering the treatment and in terms of evaluating the effect.
- The treatment approach is designed to correct the underlying genetic abnormality. Administration of SAR421869 directly into the eye provides a convenient means of delivering the normal MYO7A cDNA and so is able to restore retinal transport function resulting in a longer duration of effect, or permanent restoration of myosin VIIa protein function.
- The eye is easily accessible to safety monitoring using multiple methodologies.

4.9 RATIONALE FOR PROPOSED SUBRETINAL INJECTION SITE

In patients with RP, there exists a transition zone between normal and abnormal retina that can be defined readily on spectral domain OCT. The reduction in visual sensitivity in the transitional zone correlates well with the progressive increase in retinal degeneration, and particularly a decrease in outer nuclear layer (ONL) thickness. This zone contains normal and degenerating photoreceptors with both normal and abnormal sensitivity, and thus is a good candidate region for localized gene therapy, and to perform the retinotomy and SAR421869 bleb placement in Usher Syndrome 1B patients.

The transition zone is detectable in very early disease with the least severely affected definable region beginning at about 3 mm from the center of the fovea and extending outward, with the most severe region beyond about 8-9 mm from fixation. In more advanced stages, the first transition region begins about 2 mm or less from the fovea and the rest of the regions of transition are collapsed such that abnormally thinned outer nuclear layer (ONL) occurs by 2 to 4 mm eccentricity and the region of greatest abnormality of outer retinal layer (that of extensive retinal remodeling with profound loss or absence of photoreceptors as well as absence of sensitivity), would be reached within 5 mm or less distance from the fovea (23).

In Part A of the study patients will have a visual field in the worse seeing-eye that subtends ≤ 20 degrees on the retina. This visual field is equivalent to 3-6 mm from the center of the fovea and in the center of the transition zone of these patients. Subretinal injection in this region will be widely separated from the fovea, thus minimizing any risk to central visual acuity, but will also be in a region of the transition zone that may improve in function and where SAR421869 may give benefit.

In Parts B and C of the study patients will have much less restricted visual fields and the transitional zone will be wider (approximately 3-9 mm around the fovea) ensuring the risk to central visual acuity is further minimized by performing the subretinal injection even more distant from the fovea, but still maintaining the possibility to show benefit of SAR421869.

In addition, the placement of the retinotomy site and subretinal injection nasal to the optic disc will minimize the risk to foveal retinal function. The optic disc and superior and inferior nerve fiber layers extending from the disc will form an anatomical buffer between the injection site and the fovea, further minimizing the possibility of foveal extension and thus risk to central vision.

4.10 RATIONALE FOR UNILATERAL ADMINISTRATION

In this study the contralateral non-administered eye will act as the control (ie, intra patient control) as well as the untreated areas of the study eye. The more severely affected of the two eyes will be injected. This is done with the intention of minimizing risk to the less affected eye and thus reducing risk to the patient's remaining vision.

Species	Approximate axial ocular diameter (cm)	Approximate orbital volume (cm ³)	Relative ocular volume as compared to mouse	Safe maximal subretinal volume (µL)	Allometric scale-up based on size relative to mouse safe volumes
Mouse	0.34 (24)	0.16 (25)	-	2	-
Rat	0.64 (26)	1.1	7	10	5
Rabbit	1.5 (27)-1.6 (28)	5 (29)- 14.1	88	100 (30)	50
Macaque	1.7 (31)	20.6	129	100 (32)-150 (33)	50-75
Human	2.4 (34)	57.9	362	1000 (35),(36)	500

4.12 RATIONALE FOR DOSING INTERVALS

A single unilateral dose of SAR421869 will be administered to each study patient who completes screening. Patients with advanced RP will be included in Cohorts 1, 2 and 3. Cohort 4 (MTD adults) and Cohort 5 (MTD including pediatric patients) will include patients with less advanced RP. In the non-clinical studies bleb resolution, vector clearance and gene expression have all occurred within two weeks post administration. Therefore, allowing 21 days between dosing individual patients (Cohorts 1-3) and 28 days between patient cohorts (Cohorts 1-4), will permit adequate time to assess short-term safety, including ocular inflammation and post-operative complications prior to dose escalation or the inclusion of adult patients with less advanced disease.

Thus, prior to dose escalation there will be up to 4 month safety data on the first patient, up to three months on the second and up to one month safety data on the third patient in the preceding cohort. These data will permit assessment of the short-term safety profile during the dose escalation part of the study. In addition, the long-term safety data (approximately 12-14 months) from patients with advanced disease dosed in the first three cohorts of the study will be available at the time of treating the final, less severely affected patient groups (Cohorts 4 and 5).

Prior to the inclusion of pediatric patients ≥ 6 years of age (Cohort 5), the DSMB will review all safety data, including data from Parts A and B, three months after all 6 patients in Cohort 4 have been dosed. An interim report including all available safety data, preliminary efficacy data and the recommendations from the DSMB will be submitted to the regulatory authorities and institutional review boards/ethics committees for review, before patients 6-17 years of age can be enrolled into Part C of the study.

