This is a Phase I/Ia open label dose escalation study of subretinally injected SAR421869 in patients with retinitis pigmentosa (RP) associated with Usher Syndrome Type 1B. In this study at least three doses of SAR421869 will be evaluated over five patient cohorts. The study is separated into a dose escalation phase, Part A, followed by a two part dose extension phase at the maximum tolerated dose, Parts B and C.

Part A will evaluate at least 3 ascending dose levels of SAR421869, in 300 μ L of vehicle. A total of at least 15 patients ≥ 18 years of age will be entered: 3 patients in Cohorts 1 and 2 and at least 9 patients in Cohort 3. An interval of 21 days between dosing the first and subsequent patients will be observed in Cohorts 1-3 in order to assess the safety. If DSMB requires additional patients – total up to 24 may be included in Part A.

After dosing the last patient in each of the first three cohorts, the patients will be followed for 28 days to ensure there are no dose-limiting toxicities. If after a minimum interval of 28 days from dosing the last patient of the previous cohort, the safety and tolerability is considered satisfactory by the DSMB, then patients in the next cohort will be dosed.

If the safety and tolerability of SAR421869 is considered satisfactory by the DSMB in Part A of the study, the study will proceed to Part B.

In Part B (Cohort 4), 6 patients ≥ 18 years of age will be treated at the maximum tolerated dose (MTD) determined from Part A, to further characterize the risk: benefit profile of SAR421869. These patients will be enrolled in parallel.

Part C (Cohort 5) provides the opportunity to extend the study to include pediatric patients 6-17 years of age treated at the MTD. Prior to the inclusion of pediatric patients, the DSMB will review all safety data including the data from Part B, three months after all 6 patients in cohort 4 have been dosed. An interim report including all available safety data, preliminary efficacy data and the recommendations from the DSMB will be submitted to the regulatory authorities and institutional review boards/ethics committees for review, before up to 6 patients 6-17 years will be included in Part C of the study (Cohort 5).

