7 STUDY DESIGN

This is a Phase I/IIa, open-label, dose escalation study of subretinally injected SAR421869 in patients with Usher's RP. In this study at least three doses of SAR421869 will be evaluated over five patient cohorts stratified by disease severity and age. The study is separated into a dose escalation phase, Part A followed by a two part dose extension phase at the maximum tolerated dose, Parts B and C.

An independent data safety monitoring board (DSMB) will be convened to monitor safety and will meet regularly either at face-to-face meetings or by teleconference once the first patient has been enrolled. Based on accrual of the data, the committee will comprehensively review the safety and tolerability of the treatment for each individual patient, and make decisions regarding dose escalation, study continuance and recommended amendments to the protocol.

Part A will evaluate at least 3 ascending dose levels of SAR421869, in 300 µL of vehicle. A total of at least 15 patients (≥ 18 years of age) will be entered: 3 patients in Cohort 1 and 2 and at least 9 patients in Cohort 3. An interval of 21 days between dosing the first and subsequent patient will be observed in Cohorts 1-3 in order to assess safety. The DSMB will recommend whether to dose escalate following review of the data one month after all three patients have been dosed in each cohort in Part A. If DSMB requires additional patients – total up to 24 may be included in Part A.

If the safety and tolerability of SAR421869 is considered satisfactory by the DSMB in Part A and to further characterize the risk: benefit profile of SAR421869, the study will proceed to Part B, where 6 patients ≥ 18 years of age with less severe disease (Cohort 4) may be treated at the maximum tolerated dose determined from Part A, these patients may be enrolled in parallel.

The DSMB will review all safety data including the data from Parts A and B three months after all patients in Cohort 4 have been dosed. An interim report including all available safety data and preliminary efficacy data will be submitted to the regulatory authorities and institutional review boards/ethics committees for review, before up to 6 patients 6-17 years of age can be enrolled in Part C of the study (Cohort 5). Patients enrolled into Part C will be treated at the MTD determined from Part A of the study and further characterized in Part B of the study.

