9 TREATMENT PLAN AND METHODS

9.1 ALLOCATION OF TREATMENTS

Dose Escalation Part A

Patients will be allocated to treatment in the order in which they are enrolled into the study.

Dose escalation or progression to the next patient cohort will be based on safety in the three patients of the previous cohort, including events such as the presence and severity of manifested clinical signs and symptoms, laboratory tests including clinical chemistry, hematology, urinalysis and antibodies. The DSMB will thoroughly review and discuss the results from the previous cohort before proceeding with any subsequent dose escalation. All patients in the previous cohort must be observed for a minimum of 28 days before additional participants receive drug at the next dose level.

Dose Extension (MTD) Parts B and C

The Maximum Tolerated Dose to be used in Parts B and C (Cohorts 4 and 5) of the study will be determined from the dose escalation phase (Part A). Cohort 4 will include only adult patients (≥ 18 years or older) with less advanced RP, while Cohort 5 will provide the opportunity to include pediatric patients 6-17 years of age. Before pediatric patients can be enrolled into the study, the DSMB will review all safety data including the data from Part B, three months after all patients in Cohort 4 have been dosed. An interim report including all available safety data and preliminary efficacy data will be submitted to the regulatory authorities and institutional review boards/ethics committees for review prior to the enrolment of pediatric patients.

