In Part A of the study, a minimum interval of 21 days between the dosing of the first and subsequent patients in each cohort and a minimum interval of 28 days between cohorts has been selected in order for the DSMB to assess any acute toxicity, post-operative complications and the safety profile at each dose level of UshStat. The DSMB will be responsible for determining whether to proceed enrolling the next cohort of patients. Based on accrual of the data, the DSMB will comprehensively review the safety and tolerability of UshStat and make the decisions regarding dose escalation, study continuance, and recommended amendments to the protocol. If after a minimum interval of 28 days from the dosing of the third patient in a given cohort, the safety and tolerability is considered satisfactory by the DSMB, then the next cohort of three patients will be enrolled. The maximum tolerated dose (MTD) will be defined as the highest dose level that has an acceptable safety and tolerability and positive benefit/risk profile in the opinion of the DSMB.

If the safety and tolerability is considered satisfactory by the Data Safety and Monitoring Board (DSMB), regulatory authorities and institutional review boards (IRB) / independent ethics committees (EC) in Part A of the study, then the study will proceed to Part B that may enroll a maximum of three patients in parallel.

Patients enrolled in Part B must be at least 18 years old, have RP associated with Usher syndrome type 1B caused by *MYO7A* mutation(s), exhibit concentric constriction of kinetic visual field centrally in the worse seeing eye equating to a horizontal visual field diameter of >20 degrees confirmed by visual field measurement by Semi-automated Kinetic Perimetry (SKP), exhibit visual field loss in the worse seeing eye that is equivalent to at least 30% reduction from normal sensitivity volume (decibel-steradians) on full-field German Adaptive Thresholding Estimation (GATE) Static Perimetry using the size V test target, and have no detectable rod-derived amplitudes on full field ERG.

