Part C provides the opportunity to extend the study to include pediatric patients at least six years of age. Prior to inclusion of pediatric patients, the DSMB will review all safety data three months after all three patients in Cohort 4 have been dosed. An interim report including all available safety data, preliminary efficacy/activity data and the recommendations from the DSMB will be submitted to regulatory agencies and institutional review boards/ethics committee for review before patients of at least six years of age will be included in Part C of the study (Cohort 5).

The UshStat doses to be studied are:

Subretinal Injection				
Part A				
Cohort	Age	Number of patients	Vector total dose per eye	Volume
1	≥ 18	3	1.4×10^5 TU	300 μ L
2	≥ 18	3	4.7×10^5 TU	300 μ L
3	≥ 18	3	1.4×10^6 TU	300 μ L

Part B				
4	≥ 18	3	MTD	300 μ L

Part C				
5	≥ 6	Up to 6	MTD	300 μ L

The initial UshStat dose to be studied will be 1.4×10^5 transducing units (TU), in 300 μ L of vehicle. Dose levels will increase to a maximum of 1.4×10^6 TU. The MTD will be defined as the highest dose level that has an acceptable safety and tolerability and positive benefit/risk profile in the opinion of the DSMB.

Patients will be allocated to active treatment (UshStat), in the order in which they are enrolled into the study. A minimum of 21 days must be allowed between dosing of the first and subsequent patients in any cohort, and a minimum of 28 days must be allowed between the final patient of one cohort and the first patient of the subsequent cohort. Three patients (with 21 days of follow-up between the first and subsequent patients) will be initially enrolled into the first cohort and receive the lowest dose of study drug (1.4×10^5 TU). If the DSMB agrees safety and tolerability are acceptable for this group of patients at the lowest dose (after a minimum of 28 days), then three more patients will be enrolled into the second cohort, receiving the next dose of UshStat (4.7×10^5 TU). Patients in Cohort 3 will receive a dose of 1.4×10^6 TU of investigational medicinal product (IMP), in accordance with the procedures outlined in the preceding paragraph.

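### Section 4.12 assumes 21 days between individual Part A patients, but the synopsis separates only the first patient of a cohort from the rest

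*Protocol*

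**What the plan says.** Four places in the protocol, and the SAP, bear on spacing within a Part A cohort.

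- **Protocol 4.12 (rationale).** The interval is justified as "allowing 21 days between dosing individual patients (Cohorts 1-3"), together with 28 days between cohorts. For the follow-up in hand when the dose is raised, the section gives these ceilings: "up to 4 month safety data on the first patient, up to three months on the second and up to one month" for patient 3.
- **Protocol 1 (synopsis).** "An interval of 21 days between dosing the first and subsequent patients will be observed in Cohorts 1-3". On numbers, it gives "3 patients in Cohorts 1 and 2 and at least 9 patients in Cohort 3".
- **Protocol 7.** "An interval of 21 days between dosing the first and subsequent patient will be observed in Cohorts 1-3". The noun is now singular, so the sentence can mean either the second patient only or each next patient in turn.
- **Protocol 9.1.** "Patients will be allocated to treatment in the order in which they are enrolled into the study". It adds 28 days of observation before the next dose level but no interval within a cohort. Section 12.2, on the DSMB's duties, gives none either.
- **SAP 3.0.** "a minimum interval of 21 days between the dosing of the first and subsequent patients in each cohort", and again "A minimum of 21 days must be allowed between dosing of the first and subsequent patients in any cohort". This SAP (version 2, July 2016) describes nine Part A patients and was written before Amendment 8, so it is secondary evidence.

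**The concern.** The safety argument and the design instruction describe different rules. Section 4.12 needs a gap between patients 2 and 3. The synopsis does not ask for one, and no other section clearly does.

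The gap matters because the product cannot be taken back. Section 10.1.3 says there is no known way to remove the vector, and the amendment rationale reports a serious uveitis case in this study. Section 8.5 stops dosing after a dose-limiting toxicity, but that cannot help a patient who has already been injected. If patients 2 and 3 are dosed together, nothing learned from patient 2 can inform the decision to dose patient 3.

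Cohort 3a shows the limit of a rule tied only to the first patient. By measured strength its first patient received 0.33×10^6 TU and the next two received 2.4×10^6 TU, about seven times as much (2.4 / 0.33 = 7.3). The first patient was therefore not a sentinel for the dose the other two received, and the synopsis set no interval between those two. Their dosing dates are not given, so this shows what the wording left open and not what happened.

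**Working it through.** **Inputs**

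- Interval within a cohort: 21 days, applied to each consecutive pair (4.12) or only after the first patient (synopsis, SAP 3.0).
- Observation after the last patient before the next dose level: 28 days (synopsis, 9.1).
- One month = 28 days (synopsis, 8.2).
- Visit windows (Section 2, 9.4): Weeks 1, 2 and 4 are ±3 days; Week 12 is ±14 days.

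**The plan's own figure first.** Section 4.12 gives ceilings of 4, 3 and 1 months, which are 112, 84 and 28 days. The minimum intervals with every pair spaced give 70, 49 and 28 days, or 2.5, 1.75 and 1.0 months. Only the third figure is reproduced. The 4.12 figures are upper limits and no maximum interval is stated, so this is not a contradiction. The ceilings correspond to gaps of 112 − 84 = 28 and 84 − 28 = 56 days. That fits staggered dosing of patients 2 and 3 but does not require it.

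**Dosing calendar, patient 1 on day 0, earliest permitted days**

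| | Section 4.12 | Synopsis, read alone |
|---|---|---|
| Dosing days, patients 1 / 2 / 3 | 0 / 21 / 42 | 0 / 21 / 21 |
| Follow-up on patient 1 when patient 3 is dosed | 42 − 0 = 42 days | 21 − 0 = 21 days |
| Follow-up on patient 2 when patient 3 is dosed | 42 − 21 = 21 days | 21 − 21 = 0 days |
| Earliest next dose level | 42 + 28 = day 70 | 21 + 28 = day 49 |
| Follow-up at that point, patients 1 / 2 / 3 | 70 / 49 / 28 days | 49 / 28 / 28 days |

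**Completed scheduled post-operative visits when patient 3 is dosed.** In days after a patient's own surgery, the visits fall on Day 1, then days 4–10 (Week 1), 11–17 (Week 2), 25–31 (Week 4) and 70–98 (Week 12). By day 42 a patient has completed four, by day 21 three, and by day 0 none. No window straddles day 21 or day 42, so the counts do not depend on which end of a window is used.

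- Section 4.12: 4 + 3 = 7 visits.
- Synopsis: 3 + 0 = 3 visits.

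**Patients still exposed to the wording.** Nine patients (3 + 3 + 1 + 2) make up Cohorts 1, 2 and 3a. Part A is planned at 15 to 24, so 15 − 9 = 6 to 24 − 9 = 15 remain.

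**The case against.** The strongest reply is that the protocol as a whole does not permit same-day dosing. Section 15.8 requires every item of the protocol to be followed exactly, and 4.12 is part of it. A site that spaces every patient by 21 days satisfies both texts, whereas one that doses patients 2 and 3 together departs from 4.12. Parallel enrolment is stated only for Part B, which implies that Part A is sequential and fits the singular noun in Section 7. This stands as evidence of intent. It does not remove the drafting problem: 4.12 is a rationale section, and the design text a site would use to schedule surgery is looser.

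The risk is also bounded:

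- Patient 1 will have completed the Day 1, Week 1 and Week 2 visits before patient 2 is dosed.
- Serious events and ocular events of special interest are reported within 24 hours, and the DSMB reviews safety.
- The doses for 3b and 3c (0.33×10^6 and 1.4×10^6 TU) are below the 2.4×10^6 TU already given to two patients.
- Amendment 8 makes corticosteroid prophylaxis mandatory.

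All of these stand. So does the point that dose-limiting toxicities and suspension criteria are detailed in a DSMB charter that was not available. The adverse-event table shell attached to the 2019 memorandum shows three cohorts of three, so 3b and 3c may never have been dosed, but a table shell is not an enrolment record.

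A reader might go further and treat Cohort 3 as a single cohort whose first patient was dosed in 3a, leaving 3b and 3c with no spacing at all. The synopsis count of at least nine in Cohort 3 and one heading in Section 8.2 that calls 3b and 3c subgroups invite this. The documents do not support it. The synopsis entry criteria, the Section 2.2 schedule and both dosing tables treat 3b and 3c as cohorts. Sections 7 and 9.1 work with three patients per cohort, and the 28-day gate before 3c depends on 3b being one. Each therefore has its own first patient and at least the first-patient interval.

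**Conclusion.** The inconsistency is real and lies within the current protocol; the SAP only repeats the looser rule. Read literally and alone, the synopsis lets patient 3 be dosed 21 days earlier than 4.12 assumes, with no follow-up on patient 2. It also takes 21 days off the minimum follow-up on patients 1 and 2 before escalation.

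These figures assume dosing on the earliest permitted days, three patients per group and no further restriction in the DSMB charter. A reader might infer that same-day dosing was planned or took place. Neither document says so, and sequential dosing is the more likely intention. The correction is worth making because it is small, matches the sponsor's own rationale and protects the third patient of a group from an irreversible first-in-man exposure. Confidence is medium, because of the unseen charter and the ambiguous wording of Section 7.

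**What to change.** In Sections 1, 7 and 9.1 of the protocol, and in SAP 3.0 if it is updated for Amendment 8, state one rule: *Each Part A patient, including those in Cohorts 3b and 3c and any added patients, is dosed at least 21 days after the previous patient.* Section 4.12 then needs no change, and neither does the 28-day gate between dose levels.

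The cost is one sentence in each place and a delay of up to 70 − 49 = 21 days per group of three, or 2 × 21 = 42 days over 3b and 3c. Any further group of three would add up to 21 days. There is no delay if sites already space every patient.

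The change protects the third and later patients of a group. It does not alter the fact that patient 2 may be dosed on day 21, before patient 1 reaches the 28-day point used in the Section 8.4 stopping criterion.
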